A Randomized, Controlled Pilot Trial Assessing the Utility of Cognitive Behavioral Therapy to Improve Endothelial Function and Reduce Inflammation in Depressed, Virologically-Suppressed, Antiretroviral-Treated, HIV-infected Adults

Version 4.0
September 1, 2017

Funded by the National Institutes of Health/National Heart, Lung, Blood Institute
R01HL126557

Principal Investigators:

[name], MS
Division of Infectious Diseases
Department of Medicine
Indiana University School of Medicine

Date

[name]
Department of Psychology
Indiana University-Purdue University-
Indianapolis

Date

TABLE OF CONTENTS (MAJOR SECTIONS ONLY)

SCHEMA	Page 3
1.0 STUDY OBJECTIVES	Page 4
2.0 HYPOTHESES, BACKGROUND, AND INTRODUCTION	Page 4
3.0 STUDY DESIGN	Page 12
4.0 SELECTION AND ENROLLMENT CRITERIA	Page 15
5.0 STUDY TREATMENT	Page 17
6.0 CLINICAL AND LABORATORY EVALUATIONS	Page 18
7.0 ADVERSE EVENT MANAGEMENT	Page 22
8.0 CRITERIA FOR STUDY DISCONTINUATION	Page 23
9.0 STATISTICAL CONSIDERATIONS AND DATA MANAGEMENT	Page 23
10.0 HUMAN PARTICIPANTS RESEARCH AND PROTECTION	Page 26
11.0 REFERENCES	Page 30
APPENDIX: SUICIDE MANAGEMENT PLAN AND SUICIDIALITY FORM	Page 39

SCHEMA

DESIGN

The objectives of this study will be met by performing a 24-week, randomized, controlled, single-blinded, two-arm, parallel group, pilot trial at a single center. A total of 200 subjects may be screened to identify 110 participants to be enrolled and randomized. These participants will be ≥ 18 years old, have been receiving antiretroviral therapy for at least one year with an HIV viral load < 75 copies/mL at screening, and have major depression using the PHQ-9 questionnaire. These participants will be randomized 1:1 to either depression treatment with the Beating-the-Blues cognitive behavioral therapy program (N=55) or usual care (N=55).

OBJECTIVES

The primary objective of this study is to compare 12-week changes in flow-mediated dilation (FMD) of the brachial artery in HIV-infected, depressed adults already receiving virologically suppressive antiretroviral therapy (ART) who are then randomized to either depression treatment with the Beating the Blues (BtB) cognitive behavioral therapy program or to Usual Care (UC). Key secondary objectives include comparing changes in FMD between the two groups at 24 weeks and comparing changes in circulating IL-6, hsCRP, D-dimer, EPCs/ECFCs, and markers of monocyte activation (CD14+CD16+ cell proportions and sCD14/sCD163) at both 12 and 24 weeks.

DURATION

Each individual participant will be followed for approximately 28 weeks (up to 4 weeks from screening to randomization and 24 weeks on study). We expect to enroll 3-4 participants per month. The total duration of this study will be approximately 38 months.

POPULATION

All participants will be HIV-infected, 18 years of age or older, have achieved HIV-1 viral loads less than 75 copies/mL while receiving stable ART for at least 12 months, and have a PHQ-9 score ≥ 10 . Participants will be recruited from the infectious diseases outpatient clinics of Eskenazi Health Hospital and the Indiana University Health Hospitals.

SAMPLE SIZE

The total sample size for this study will consist of 110 enrolled participants. Up to 200 participants may be screened to identify the 110 eligible for enrollment. If a consented and otherwise eligible participant withdraws prior to the Baseline/Entry Visit, this participant will be replaced.

1.0 STUDY OBJECTIVES

1.1 Primary Objective

1.1.1 To compare 12-week changes in FMD between those undergoing depression treatment using the Beating the Blues (BtB) program vs those receiving Usual Care (UC).

1.2 Secondary Objectives

1.2.1 To compare 24-week changes in FMD between those undergoing depression treatment using BtB vs those receiving UC.

1.2.2 To compare 12 and 24-week changes in circulating levels of IL-6, hsCRP, D-dimer, fasting lipid profiles (total cholesterol, HDL-C, LDL-C, triglycerides), insulin resistance estimated using HOMA-IR, systolic and diastolic blood pressures, body mass indices (BMI), circulating EPC/ECFC levels, and circulating markers of monocyte activation (CD14+CD16+ cell proportions and sCD14/sCD163) between those undergoing depression treatment using BtB vs those receiving UC.

1.2.3 To compare 12 and 24-week changes in PHQ-9 scores and SCL-20 scores between those undergoing depression treatment using BtB vs those receiving UC.

1.2.4 To correlate FMD, IL-6, hsCRP, D-dimer, circulating EPCs/ECFCs, and markers of monocyte activation (CD14+CD16+ cell proportions and sCD14/sCD163) levels with PHQ-9 and SCL-20 scores at baseline.

1.2.5 To assess the safety, HIV-1 RNA levels, and CD4 cell counts of the BtB program in HIV-infected adults.

1.2.6 To explore the relationships between genetic markers with FMD, PHQ-9, SCL-20 scores at baseline and with response to depression treatment with BtB.

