4.2 Exclusion Criteria

4.2.1 Inability to complete written, informed consent.

4.2.2 Incarceration at the time of any study visit.

4.2.3 Active suicidality, as determined by the patient's HIV provider or social worker following a positive response (1, 2, or 3) to PHQ-9 Item #9 and a positive response (yes) to one or more of the three questions (for Question #3, the previous attempt must be within the past 10 years) on the Patient Suicidality Form (see Appendix).

4.2.4 Diagnosed vascular disease (documented history of angina pectoris, coronary disease, peripheral vascular disease, cerebrovascular disease, aortic aneurysm, or otherwise known atherosclerotic disease).

4.2.5 History of congestive heart failure, even if currently compensated.

4.2.6 Diagnosed disease or process, besides HIV infection, associated with increased systemic inflammation (including, but not limited to, systemic lupus erythematosus, inflammatory bowel diseases, other collagen vascular diseases).

Note: Hepatitis B or C co-infections are NOT exclusionary

4.2.7 Known or suspected malignancy requiring systemic treatment within 180 days of screening.

NOTE: Localized treatment for skin cancers is not exclusionary.

4.2.8 History of Raynaud's phenomenon.

4.2.9 History of cardiac arrhythmias or cardiomyopathy.

4.2.10 Uncontrolled hyperthyroidism or hypothyroidism, defined as TSH values outside of the local reference range on most recent clinical assessment.

4.2.11 History of carotid bruits.

4.2.12 Systolic blood pressure > 160 mmHg or diastolic blood pressure > 110 mmHg at screening.

4.2.13 Screening estimated glomerular filtration rate (eGFR) < 50 mL/min/1.73m² (calculated from the 2009 CKD-EPI equation) using a serum creatinine level measured at screening.

4.2.14 Screening glucose ≥ 140 mg/dL or hemoglobin A1c > 8.0%.

4.2.15 Screening total cholesterol > 240 mg/dL.

4.2.16 Therapy for serious medical illnesses within 14 days prior to screening.

Note: Therapy for serious medical illnesses that overlaps with a main study visit will result in postponement of that study visit until the course of therapy is completed; postponement outside of the allowed study visit timeframe will result in study discontinuation.

- 4.2.17 Pregnancy or breastfeeding during the course of the study.
- 4.2.18 Receipt of investigational agents, cytotoxic chemotherapy, systemic glucocorticoids (of any dose), or anabolic steroids at screening.

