5.2 Prohibited Medications

- Agents with significant anti-inflammatory activity (including, but not limited to, plaquenil, infliximab, etanercept, mycophenolate mofetil, sirolimus, tacrolimus, cyclosporine, pentoxifylline, theophylline, thalidomide)
- Investigational agents
- Cytotoxic chemotherapy
- Systemic glucocorticoids (topical steroids are allowed; inhaled/nasal steroids are allowed only if the participant is not also receiving HIV protease inhibitors)
- Anabolic steroids (physiologic testosterone replacement therapy is not exclusionary)

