6.0 CLINICAL AND LABORATORY EVALUATIONS

6.1 Schedule of Events

Evaluation	Screening Visit	First Entry Visit (within 15 days of Screening)	Second Entry Visit #2 (within 30 days after Screening)	Weekly BtB Sessions for the intervention group (8 in total)	Week 12 Visit (for both groups; 84-105 days after Second Entry Visit)	Week 24/Closeout Visit (for both groups; 168-189 days after Second Entry Visit)
Informed Consent	X					
Documentation of HIV Status	X					
Medical/Psychiatric History	X					
Medication/Supplement Use History	X					
Updated Psychiatric Management			X		X	X
Concomitant/Updated Medications			X		X	X
PHQ-9 Assessment	X	X	X	X	X	X
Signs & Symptoms	X		X		X	X
Diagnoses/Updated Diagnoses	X		X		X	X
Height		X				
Weight		X	X		X	X
Vital Signs	X	X	X		X	X
Brief Physical Examination	X	X	X		X	X
Urine Pregnancy Test	X	X	X		X	X
Randomization			X			
Serum chemistries/glucose, total cholesterol (non-fasting)	X					
Hematology, hemoglobin A1c	X					
HIV-1 RNA level	X		X		X	X
CD4 cell count			X		X	X
Whole blood for ECFCs and monocyte subsets		X	X		X	X
DNA sampling			X			
Beating the Blues Behavioral Intervention				X		
Questionnaires			X		X	X
FMD/NTGMD		X	X		X	X
Frozen Serum for Batched Testing of Inflammatory/Coagulation Markers, Metabolic Markers		X	X		X	X
Frozen Plasma, Serum, and Urine for Future Studies		X	X		X	X

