9.5 Analysis Datasets

Datasets	Definition
Intention-to-treat (ITT)	This will comprise all patients who meet the eligibility criteria and are randomized onto the study irrespective of their compliance to the planned course of treatment.
Per Protocol Set	This will comprise all UC patients and BtB participants who finish at least 6 out of 8 sessions.
Safety	This will comprise the BtB patients that attend at least one session of treatment.

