9.11 Analysis Plan for Secondary Objectives

Both unadjusted comparisons and adjusted comparisons between UC and BtB will be performed for secondary outcomes defined in 1.2.1-1.2.3. For adjusted comparisons, multiple linear regression models will be constructed to include treatment group, baseline characteristics [demographics, SCL-20 scores, tobacco/exercise/adherence questionnaire results, ART drugs/regimens (including efavirenz (142-144)), antidepressant use, co-morbidities, CD4 cell counts, and HIV-1 RNA levels], and time-varying characteristics (changes in SCL-20 scores, questionnaire results, CD4 cell counts, ART drugs/regimens, HIV-1 RNA levels) to determine their effects on the outcomes. Pearson and Spearman correlation coefficients will be estimated for FMD, IL-6, hsCRP, D-dimer, circulating EPCs/ECFCs levels, and markers of monocyte activation (CD14+CD16+ cell proportions and sCD14/sCD163) with PHQ-9 and SCL-20 scores at baseline. These analyses will be performed for both the intent-to-treat set and the per-protocol set. Dose-response relationships between 12- and 24-week FMD and the number of BtB sessions, which have a range from 0 to 8, will be explored.

Safety assessments will be performed using the safety dataset. HIV-1 RNA levels and CD4 cell counts of the BtB arm during the trial will be summarized and compared to the UC arm.

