10.2 Risks to the Participants

10.2.1 Human Participants Involvement and Characteristics

- A total of 110 HIV-infected participants will be recruited to participate in this pilot trial investigating the efficacy of cognitive behavioral therapy using the Beating the Blues computer program to reduce inflammation and improve endothelial function.
 - Participants must be at least 18 years of age, have documented HIV infection, have a screening HIV-1 RNA level <75 copies/mL while on ART for at least one year, and have a screening PHQ-9 score ≥ 10 .
 - The chief exclusion criteria include known CVD, congestive heart failure, treatment for malignancy (besides localized skin cancers) within 6 months of screening, uncontrolled diabetes (defined as screening Hgb A1c >8.0%) or newly diagnosed glucose intolerance (defined as screening glucose ≥ 140 mg/dL), uncontrolled hypertension (systolic BP >160 mmHg or diastolic BP >110 mmHg), screening eGFR <50mL/min/1.73² (using the 2009 CKD-EPI creatinine formula), screening total cholesterol >240 mg/dL, pro-inflammatory conditions besides HIV infection (e.g. autoimmune diseases, but allowing hepatitis B or C co-infection).
 - Potential participants will be recruited from the HIV outpatient clinics of Indiana University Health Hospitals and Eskenazi Health Hospital. All biologic/physiologic study procedures will occur in the Indiana Clinical Research Center at Indiana University Health University Hospital.

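### HOMA-IR change is compared in all participants, but eligibility allows insulin-treated diabetes, in which HOMA-IR cannot be read as insulin resistance, and no handling rule is given

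*Combined protocol and SAP*

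**What the plan says.** **Endpoint.** Section 1.2.2 lists 12- and 24-week change in "insulin resistance estimated using HOMA-IR" among the secondary outcomes, with no limit on who contributes.

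**Analysis.** Section 9.11 states: "Both unadjusted comparisons and adjusted comparisons between UC and BtB will be performed for secondary outcomes defined in 1.2.1-1.2.3". For the adjusted part, "multiple linear regression models will be constructed to include treatment group, baseline characteristics" and time-varying ones. Co-morbidities are on the covariate list; insulin use is not. The analyses run in both the intention-to-treat and per-protocol sets. Section 9.5 defines the former thus: "This will comprise all patients who meet the eligibility criteria and are randomized onto the study". The latter depends only on the number of sessions completed. Neither refers to diabetes or its treatment.

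**Who can enter.** The glycaemic exclusion in Section 4.2.14 is "Screening glucose ≥ 140 mg/dL or hemoglobin A1c > 8.0" percent. Section 10.2.1 describes the A1c limit as marking uncontrolled diabetes and the glucose limit as marking newly diagnosed glucose intolerance. Insulin is not among the agents in Section 4.2.18, nor in Section 5.2, which begins with "Agents with significant anti-inflammatory activity" and goes on to investigational, cytotoxic, glucocorticoid and anabolic agents.

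**Measurement.** The Schedule of Events has only "Frozen Serum for Batched Testing of Inflammatory/Coagulation Markers, Metabolic Markers". The insulin assay and the HOMA-IR formula are not given.

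**General safeguard.** Section 9.1 provides for a normality check, with nonparametric methods if it fails.

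**The concern.** HOMA-IR is the scaled product of fasting glucose and fasting insulin. It stands for insulin resistance only if the fasting insulin is the body's own response to the fasting glucose. Under injected insulin that link is broken, so the number no longer measures the endpoint. This is true whichever assay is used. Whether the assay also detects the injected insulin is a further question that the documents leave open.

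Followed as written, the plan puts such values into the between-arm comparison beside valid ones. Two things are at stake. The estimate mixes a measure of insulin resistance with something else. The values may also be large and erratic, which would widen the error variance of an analysis on the raw scale. If no rule is set in advance, whether to keep an extreme HOMA-IR value would have to be decided after the data are seen.

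**Working it through.** **1. The plan's own figure.** Section 9.3 gives 44 per arm, raised to 110, for FMD. With d = 0.61, power 0.80 and two-sided alpha 0.05, n per arm = 2(1.960 + 0.842)²/0.61² = 42.2, so 43. The t-based solution is 43.17, so 44. Then 88/(1 − 0.20) = 110. The figure reproduces. The 0.61 SD statement for secondary outcomes covers Week 24 FMD, IL-6, hsCRP and D-dimer. No detectable effect is stated for HOMA-IR.

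**2. Eligibility.** A person with known diabetes on insulin, with A1c of 8.0% or less and screening glucose below 140 mg/dL, meets none of the exclusions in 4.2.14 or 4.2.18 and takes nothing listed in 5.2. That person is eligible, belongs to the intention-to-treat set, and contributes HOMA-IR under 9.11.

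**3. How many.** The documents give no figure. If a fraction p of enrollees uses insulin (assumed), the chance of at least one among 110 is 1 − (1 − p)^110:

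| assumed p | chance of at least one |
|---|---|
| 0.5% | 42% |
| 1% | 67% |
| 2% | 89% |

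**4. Size of the values (assumed inputs).** HOMA-IR = glucose (mg/dL) × insulin (µU/mL)/405.
- Non-user: 90 × 10/405 = 2.2.
- User at glucose 130 with measured insulin of 20, 50 or 100: 6.4, 16 or 32.

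**5. Effect on the comparison (simulation; all HOMA-IR inputs assumed).** There are 44 per arm. Non-users are log-normal with median 2.2, log-SD 0.5 and baseline-to-follow-up correlation 0.7. The treatment effect is −0.6 units. Users have glucose 90–139 and insulin 20–100, drawn afresh at each visit, with no treatment effect. Raw-scale ANCOVA on baseline stands in for the adjusted linear regression of 9.11, and a Mann-Whitney test on change for the nonparametric fallback of 9.1.

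| insulin users among 88 | ANCOVA power | Mann-Whitney power |
|---|---|---|
| 0 | 0.80 | 0.84 |
| 1 | 0.66 | 0.85 |
| 2 | 0.53 | 0.82 |
| 3 | 0.41 | 0.80 |
| 4 | 0.31 | 0.77 |

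The ANCOVA standard error rises from 0.21 with no users to 0.26, 0.32, 0.37 and 0.43 with one to four. A Shapiro-Wilk test on the ANCOVA residuals rejects normality in at least 87% of runs even with no users, so the fallback would usually be triggered.

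**6. A second set of assumptions.** Here the median is 2.5, the log-SD 0.6 and the effect −0.25 on the log scale. Users' values run from 3 up to 20, 40 or 60.

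| insulin users among 88 | ANCOVA on raw values | Mann-Whitney | t-test on log change |
|---|---|---|---|
| 0 | 0.70–0.72 | 0.65–0.66 | 0.76–0.78 |
| 1 | 0.42–0.51 | 0.63–0.64 | 0.73–0.75 |
| 2 | 0.19–0.51 | 0.59–0.63 | 0.70–0.75 |

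**7. Type I error.** With no true effect, rejection rates were 0.036–0.050 for raw-scale ANCOVA under the inputs in step 5. They were 0.019–0.057 across all tests under those in step 6. There is no inflation.

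**The case against.** The strongest reply is Section 9.1. Normality would usually be rejected for HOMA-IR, the plan would move to ranks, and one or two insulin users would then cost only a few points of power. This stands for the unadjusted comparison. It does not settle the matter. Ranking a value that does not measure the endpoint does not make it valid. Section 9.11 also names linear regression for the adjusted comparison, without a log scale. Having co-morbidities among its covariates may absorb a shift in mean, but neither restores the meaning of the values nor removes their extra variability.

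A second reply is that few such participants are likely. The screening glucose need not be fasting (Sections 3.2 and 6.1), so a limit of 140 mg/dL screens out much treated diabetes. That is fair. The number may be zero, and every power figure above is conditional on it.

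A reader might also infer four stronger points that the documents do not support:
- *One or two insulin users would swamp the HOMA-IR result.* This is plausible only on the raw scale with large values, not under the rank fallback.
- *The stated ability to detect 0.61 SD is lost.* Section 9.3 does not make that statement for HOMA-IR.
- *A chance imbalance of insulin users would produce a false finding.* The simulations show lost precision, not excess false positives.
- *The measured insulin includes the injected drug.* That depends on an assay and an insulin type that are not given.

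**Conclusion.** The point holds as a limited defect in one secondary endpoint. The documents alone establish that HOMA-IR is compared without restriction, that insulin-treated controlled diabetes is eligible, and that no rule covers it. That HOMA-IR is not interpretable as insulin resistance in those participants follows from what the index assumes, and does not depend on how many enrol.

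The size is uncertain. The loss of precision falls mainly on the raw-scale adjusted regression: from 0.80 to about 0.66 with one user and 0.53 with two, using assumed values and ANCOVA as a stand-in. The unadjusted comparison is largely protected if the Section 9.1 fallback is applied. HOMA-IR does not appear in the hypotheses of Section 2.1, the key secondary objectives in the schema, or the power statement. The primary FMD analysis and the sample size are unaffected.

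**What to change.** Add to Section 9.11:
- The main HOMA-IR comparison is made in participants not using insulin at the Second Entry Visit, as established before randomization, and is analysed on the log or rank scale in both the unadjusted and adjusted comparisons.
- The all-participant result is reported as a sensitivity analysis.
- The number starting insulin on study is reported by arm, and a named sensitivity analysis deals with their later values. These values should not be silently dropped from the main comparison: that would condition on an event after randomization. If a sensitivity analysis sets them to missing, it should say how they enter the multiple imputation of Section 9.14.

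It would also help to name the insulin assay and the HOMA-IR formula.

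No new data are needed. Medications are recorded at screening, updated at the Second Entry Visit, and then logged with start and stop dates (Sections 6.1, 6.2.3 and 6.2.5). Restricting on a pre-randomization fact keeps the randomized comparison. The cost is a few participants in one secondary outcome. Leaving out two of 88 gives 43 per arm, which still has power of about 0.80 for a 0.61 SD difference, used here only as a yardstick.

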2.0 HYPOTHESES, BACKGROUND, AND INTRODUCTION

2.1 Hypotheses

2.1.1 Treatment with BtB will improve FMD, increase circulating EPC/ECFC levels, and reduce circulating levels of IL-6, hsCRP, D-dimer, and markers of monocyte activation (CD14+CD16+ cell proportions and sCD14/sCD163) at both 12 and 24 weeks when compared to UC.

2.1.2 Treatment with BtB will improve PHQ-9 and SCL-20 scores at both 12 and 24 weeks when compared to UC.

2.1.3 Treatment with BtB will be safely tolerated and have no effects on HIV-1 RNA suppression or CD4 cell counts.

2.1.4 Genetic variation is associated with endothelial function, depression severity, and response to depression treatment.

2.2 Background

2.2.1 HIV and cardiovascular events

Cardiovascular disease (CVD) has emerged as a leading cause of death in the HIV-infected population receiving ART (1). Given that lifespans of the HIV-infected population are nearing those of the uninfected population with the widespread use of ART (2-5), there is growing concern that the risk of HIV-CVD will be magnified several-fold worldwide, especially as the population ages (6). Although previously attributed to the dysmetabolic effects of ART, the greater risk of CVD in HIV remains, even when newer ART drugs are used that do not induce severe dyslipidemia, hypertension, or insulin resistance (7). Attention has thus turned to HIV-specific mechanisms as potential explanations for HIV-CVD. In fact, elevated markers of generalized inflammation (IL-6, hsCRP) and coagulation (D-dimer) have been found to predict HIV-CVD events (8-11). HIV may also be associated with impaired endothelial function (12, 13), perhaps due to this dysregulated inflammation and coagulation (14).

One possible etiology of the heightened inflammation, altered coagulation, and endothelial dysfunction in HIV, and consequently of the increased risk of HIV-CVD, may be depression. Depression is an independent predictor of incident CVD in the general population (15) with heightened inflammation (16), altered coagulation (17-19), and endothelial dysfunction (20-23) among the leading candidate mechanisms underlying this relationship. Thus, it stands to reason that depression may contribute to or exacerbate these pathways in HIV and thus increase the risk of HIV-CVD. Indeed, our preliminary data (section c1) indicate that depressive disorders independently increase the risk of incident acute myocardial infarction (MI) in HIV-infected veterans. However, it is unknown if depression leads to HIV-CVD through inflammatory, coagulatory, and/or endothelial dysfunction pathways. It is also unknown if depression treatments (antidepressants and/or psychotherapy) modulate these pathways and, therefore, may be useful as HIV-CVD primary prevention therapies.

It is important to note that there are as yet no definitive studies demonstrating that lowering systemic inflammation or coagulation reduces HIV-CVD events in those already on ART (12, 24, 25). Although pharmacological studies of low-dose methotrexate and ‘statins’ are underway to address this issue, it is not known if such interventions will be beneficial. Even if these interventions are found to be successful, they may be associated with adverse events, drug interactions, and increased cost when provided over the years to decades required to prevent CVD events in the aging HIV-infected population.

